4 STUDY DESIGN

This is a Phase 1, single center, dose escalation and dose expansion study of subjects with locoregionally recurrent head and neck cancer who may also have distant metastatic disease. All subjects will receive a dosimetry test dose of CLR 131 (flat dose of 15 mCi) to establish drug uptake by the tumor.

Subjects who have tumor uptake of the CLR 131 dosimetry test dose as determined on SPECT/CT imaging by the study radiologist will be eligible to participate on the treatment portion of this clinical trial. Any subject who demonstrates tumor uptake of CLR 131 by SPECT/CT imaging after the test dose will continue to participate in the treatment portion of the study. Up to six participants who do not demonstrate tumor uptake of CLR 131 by SPECT/CT will also continue with the treatment portion of the study. Based on prior experience of subjects receiving CLR 131, 75 % of eligible subjects are estimated to demonstrate CLR 131 uptake within their tumors.

Subjects showing uptake will receive a cumulative tumor dose of 60-70 Gy using personalized dose calculation of CLR 131 (via Monte Carlo) combined with external beam radiation. If the Monte Carlo dose estimate for any subject is greater than 60 Gy for the 2 doses of CLR 131 (highly unlikely based on preliminary data), then no additional external beam dose will be administered.

All subjects will start thyroid-protection medication the day prior to the CLR 131 dosimetry test dose and will continue to take thyroid protection medication for 14 days after the last CLR 131 dose.

Treatment Plan

Enrollment will start at dose level 1. Subjects will receive 2 doses of CLR 131 intravenously with the first dose on day 1 followed by the second dose on day 8. The dose of CLR 131 will be based on the dose escalation schema.

Dose Escalation Schema	
Dose Level	Doses** of CLR 131
-1*	12.5 mCi/m ²
1	15.6 mCi/m ²
2	18.75 mCi/m ²

*Dose level -1 is the de-escalation dose. The first four patients will be given Dose 1. Dose -1 will only be used if toxicities warrant de-escalation.

** Dose level listed is administered first on day 1 and again on day 8.

SPECT/CT imaging will be performed on days 2, 3, 4-6, and 7-8 of the treatment period to visualize and quantitate the biodistribution of CLR 131. Using the SPECT/CT imaging scans, the [name] lab will perform the Monte Carlo calculations to predict absorbed dose of CLR 131 to tumors and normal structures.

Based on the calculated absorbed dose of CLR 131 to the specific targeted tissue, the subject will undergo EBRT to complete the designated radiation dose outlined in the re-irradiation plan.

At baseline, 3, 6 and 12 months post completion of EBRT, subjects will be assessed for changes to head and neck specific subject health-related measures: quality of life and salivary flow rate. Swallow function will be assessed at baseline, 3 and 6 months post completion of EBRT (standard of care Modified Barium Swallow (MBS) and research-related oral profile exam) see Schematic of Study Design).

Enrollment to the study is anticipated to take approximately 20 months. Each subject will participate for approximately 27 months, although only about four months will be active participation. Details of the study schedule, including lab draws and specific study procedures are provided in section 7.

Incomplete dosing of CLR 131 within study timeframe:

In the event a participant is unable to receive the full study course of CLR 131 within the study timeframe such as a delay in drug manufacturing, the study team will evaluate if it is in the best interest of the study participant to continue with protocol therapy. If it is deemed appropriate for the subject to continue with the CLR 131 administration, their scheduled appointments, labwork and SSKI administration will be adjusted appropriately to accommodate the delay. If it is deemed in the participant's best interest to proceed to SOC EBRT, the following scenarios will occur:

- Only test dose (15 mCi) CLR 131 administered:
 - Continue SSKI until 14 days post CLR 131 administration
 - Proceed with EBRT and SOC follow-up.
- If test dose and a single therapeutic dose are administered:
 - Continue with SSKI until 14 days post CLR 131 administration
 - Undergo imaging for calculations of EBRT dose de-escalation
 - Proceed to EBRT
 - Modify EBRT dose based on the single therapeutic injection
 - Continue follow-up per protocol.

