6.7 SPECT/CT Dosimetry Evaluation

6.7.1 *Tumor and Organs at Risk (OAR) Dosimetry*

Subjects will obtain SPECT/CT images of the tumor and organs at risk at sequential imaging time points (days 2, 3, 4-6, and 7-8) after administration of the first treatment dose of CLR 131.

SPECT/CT images of tumor and organs at risk will be reconstructed using quantitative SPECT reconstruction methods with compensation for attenuation, scatter and the full collimator-detector response including septal penetration and scatter. A registered CT image will be used as the attenuation map for the SPECT images. Image data will be converted to activity per cubic centimeters using a sensitivity measurement made using a point source in air. For studies where the count rate is such that greater than 5% count rate losses are expected, deadtime corrections will be applied. The time activity curve in each pixel will be computed and fit with a mono-or bi-exponential function when possible or a piece-wise linear fit when more advanced fitting options are not possible. The fits will be integrated and divided by the injected activity to provide a 3D residence time image. This will be converted to a dose image using the RAPID Monte Carlo dose estimation code (A. Besemer & [name], 2014; A. E. Besemer *et al.*, 2017; A. E. Besemer *et al.*, 2018). The average dose and 3D dose distribution in each tumor and organs at risk will then be computed inside volumes-of-interest defined using CT and SPECT images.

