6.8 External beam radiation therapy (EBRT)

External beam radiation therapy will be used in combination with CLR 131 infusions to deliver a total dose of 60-70 Gy to the recurrent tumor in subjects determined by study radiologist to exhibit uptake of CLR 131.

The standard of care radiation therapy for this patient population is 60-70 Gy absorbed dose, irrespective of radiation delivery. Therefore, as long as the SOC radiation dose parameters are met, EBRT described in 6.8 is considered within standard of care. The total dose (60-70 Gy) delivered to the recurrent tumor will be at the discretion of the treating Radiation Oncologist.

6.8.1 *Dose specifications and target definition*

The recurrent gross tumor volume (rGTV), as defined by diagnostic imaging including CLR 131 uptake imaging and physical exam findings, will receive daily fractions of 2.0-2.5 Gy. The rGTV

will undergo a geometric expansion of 3-5 mm to create the recurrent clinical target volume (rCTV), which accounts for coverage of areas at high-risk for harboring subclinical disease. The rCTV can be modified by the treating Radiation Oncologist to account for areas thought to be free of disease (e.g. air space, bone). The rCTV will be expanded by 2-3 mm to create a recurrent planning target volume (rPTV). Elective treatment volumes treated to lower dose are generally discouraged but permitted at the discretion of the treating physician.

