6.8.4 Definition of organs at risk and recommended dose constraints

Organs at risk (OARs) in subjects undergoing re-irradiation may have already approached or exceeded their respective recommended dose limitation. For example, during the initial treatment course, one or both parotid glands may have already exceeded the recommended dose of less than 26 Gy. Therefore, in situations such as these, best clinical judgement will be exercised by the treating radiation oncologist for dose constraints.

The concept of dose forgiveness with regard to the time from prior radiation to re-irradiation, especially for critical structures such as the spinal cord, will be taken into account by the treating Radiation Oncologist when deciding on final OAR doses.

Recommended dose to OAR may or may not be achievable based upon the prior radiation and contribution of CLR 131 to the total dose.

Spinal cord: The spinal cord begins at the cranial-cervical junction (i.e. between the foramen magnum and the top of the C1 vertebral body). Superior to this is the brainstem and inferior is the spinal cord. The inferior border of the spinal cord is at approximately T3-4 (i.e. 2 cm below the lowest slice containing rPTV). The spinal cord will be defined based on the treatment planning CT scan. All attempts to limit the combined total dose from the previous and current radiation treatment regimen (CLR 131 and EBRT) to less than 60 Gy will be made. Higher point doses can

be considered and are at the discretion of the treating physician, however the spinal cord maximum point dose including prior radiation course will not exceed 65 Gy.

Brainstem: The inferior most portion of the brainstem is at the cranial-cervical junction between the foramen magnum and top of the C1 vertebral body. The brainstem will be contoured to the level of the posterior clinoid. The brainstem will be defined based on the treatment planning CT scan. All attempts to limit the combined total dose from the previous and current radiation treatment regimen (CLR 131 and EBRT) to less than 70 Gy will be made. Higher point doses can be considered and are at the discretion of the treating physician, however the brainstem maximum point dose including prior radiation course will not exceed 72 Gy.

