14.2 Sample Size Considerations

An mTPI-2 design, an extension of modified toxicity probability interval (mTPI-2), will be used to identify the MTD using cohorts of 4 subjects and up to 3 dose levels of CLR 131 (Ji *et al.*, 2007; Ji & Wang, 2013). The first 4 subjects will be treated at Dose Level 1. The maximum number of subjects treated at a dose level will be 8, with one exception: if 1 out of 8 subjects experiences a DLT at Dose Level 1, the study team will consider the possibility of treating 2 additional subjects at Dose Level 1. The trial can be monitored using columns 4 and 8 of [Table 3](#) below, which contains the dose-escalation rules. Dose escalation will not be confirmed until all subjects in cohort recover to non-DLT levels or meet the criteria above. If 0 out of 4 subjects experiences a DLT at Dose Level 2, the study will move directly to the expansion phase.

Dose Level	Doses* of CLR 131
-1	12.5 mCi/m ²
1**	15.6 mCi/m ²
2	18.75 mCi/m ²

*Dose level listed is administered on first on day 1 and again on day 8.

**The first 4 subjects will be treated at dose level 1. Dose level -1 will be used as a de-escalation dose.

Table 3: Dose escalation rules

	1	2	3	4	5	6	7	8	9	10
0	E	E	E	E	E	E	E	E	E	E
1	D	D	D	S	S	S	S	S	S	E
2		DU	DU	D	D	D	S	S	S	S
3			DU	DU	DU	DU	D	D	D	D
4				DU	DU	DU	DU	DU	DU	D
5					DU	DU	DU	DU	DU	DU
6						DU	DU	DU	DU	DU
7							DU	DU	DU	DU
8								DU	DU	DU
9									DU	DU
10										DU

Column indicates the number of subjects treated. Row indicates the number of subjects with DLTs. **E**: Escalate to the next higher dose; **S**: Stay at the same dose; **D**: De-escalate to the previous lower dose; **DU**: De-escalate to the previous lower dose and the current dose will never be used again in the trial; sample size = **10**, target toxicity probability = **0.2**, epsilon 1 =**0.1**, epsilon 2 =**0.1**.

The number of participants treated in the expansion cohort is dependent on the number of participants treated at the MTD in the dose escalation phase using the the mTPI-2 design. Up to 12 subjects will be treated at the MTD. Statistical analysis for outcomes is based on participants treated at the MTD, including dose escalation patients treated at the MTD.

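### Two stated rules for setting the external beam dose count only the treatment doses of CLR 131 and leave out the 15 mCi test dose that every subject receives

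*Combined protocol and SAP*

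**What the plan says.** Section 4 gives all subjects a flat 15 mCi test dose and then two treatment doses, on day 1 and day 8. The calculated CLR 131 dose to the target decides how much EBRT is added. Three rules in that section bear on the test dose:

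- No EBRT is given if the Monte Carlo estimate is "greater than 60 Gy for the 2 doses of CLR 131". The section defines the two doses as day 1 and day 8.
- After the test dose and one treatment dose: "Modify EBRT dose based on the single therapeutic injection".
- After the test dose alone: "Proceed with EBRT and SOC follow-up", with no EBRT adjustment stated.

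The dose-level table in Section 4 carries the note "Dose level listed is administered first on day 1 and again on day 8". The table in Section 14.2 has the same content: "Dose level listed is administered on first on day 1 and again on day 8".

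Other wording is more general. Section 6.8 uses EBRT "in combination with CLR 131 infusions to deliver a total dose of 60-70 Gy". Section 6.8.4 sets cord and brainstem limits on the sum of previous radiation, CLR 131 and EBRT.

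Section 6.7.1 takes the dosimetry from scans after the first treatment dose: "The fits will be integrated and divided by the injected activity to provide a 3D residence time image". It describes no correction for test-dose activity still present, and no scaling from one dose to two.

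**The concern.** The test dose is the same drug and isotope as the treatment doses, and it irradiates the same tumor and organs. If it is not counted, the EBRT top-up is calculated from an incomplete CLR 131 dose, and the total delivered differs from the total prescribed. These are previously irradiated patients, and the CLR 131 dose is also a term in their cord and brainstem totals, so the plan should say which administrations count.

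The dose-limiting toxicity data likewise come from two labelled doses plus 15 mCi, while both dose-level tables name only the two doses.

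**Working it through.** **Inputs.** Test dose 15 mCi (Section 4). Level 1 is 15.6 mCi/m² and Level 2 is 18.75 mCi/m², each given twice (Sections 4 and 14.2). The interval from test to treatment dose (the gap) is 7-14 days, up to four weeks (Section 7.2.1). The I-131 physical half-life is 8.02 days (Section 6.1). BSA is capped at 2.5 m² (Section 6.2). Actual BSA values are not given, so I assume 1.5-2.5 m², with 2.0 m² for the worked case.

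**Activity.** The two-dose totals implied by the tables are 2 × 15.6 = 31.2 and 2 × 18.75 = 37.5 mCi/m². The test dose adds 15/BSA, which is 6.0 mCi/m² at BSA 2.5 and 10.0 at BSA 1.5. Totals given are therefore 37.2-41.2 mCi/m² (Level 1) and 43.5-47.5 mCi/m² (Level 2).

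**Tumor dose.** Assume the same Gy per mCi and the same kinetics for each administration. Let A1 be the first treatment activity: 15.6 × 2.0 = 31.2 mCi. Let f be the fraction of the test dose's cumulated activity still to come on day 1. Scans after dose 1 then reflect A1 + 15f.

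- One treatment dose: shortfall = 15(1 − f)/(15 + A1) = 15(1 − f)/46.2.
- Two treatment doses, if the dose-1 estimate is simply doubled (the plan does not say): shortfall = 15(1 − 2f)/(15 + 2A1) = 15(1 − 2f)/77.4.

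Three kinetic cases were run:

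- Prompt uptake with physical decay: f = 2^(−gap/8.02).
- Slow uptake: activity proportional to (1 − 2^(−t/2)) × 2^(−t/8.02), with an assumed 2-day uptake half-time.
- Faster clearance: prompt uptake with an assumed 5-day effective half-life.

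| Gap | Case | f | One dose | Two doses |
|---|---|---|---|---|
| 7 d | Slow uptake | 0.670 | 10.7% | −6.6% |
| 7 d | Prompt | 0.546 | 14.7% | −1.8% |
| 7 d | 5-day | 0.379 | 20.2% | +4.7% |
| 14 d | Slow uptake | 0.372 | 20.4% | +5.0% |
| 14 d | Prompt | 0.298 | 22.8% | +7.8% |
| 14 d | 5-day | 0.144 | 27.8% | +13.8% |
| 28 d | Slow uptake | 0.111 | 28.9% | +15.1% |
| 28 d | Prompt | 0.089 | 29.6% | +15.9% |
| 28 d | 5-day | 0.021 | 31.8% | +18.6% |

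Positive values mean that the dose is understated, as a percentage of the dose from all CLR 131 given. With no residual in the scans (f = 0) the shortfalls are 15/46.2 = 32.5% and 15/77.4 = 19.4%.

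The one-dose error is positive whenever f is below 1, so its direction is fixed. The two-dose error changes sign at f = 0.5, which is a gap of 8.0 days with prompt uptake and 10.6 days with slow uptake. Both lie inside the target window.

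**The case against.** The strongest reply is that the plan does not exclude the test dose from the quantities that matter most. Section 4 speaks of a cumulative tumor dose, and the wording of Sections 6.8 and 6.8.4 is broad enough to include it. The Protocol Summary says the test dose serves to enable Monte Carlo estimation. The reference to a single injection may only mean one treatment dose rather than two. This stands as far as it goes: a reader might infer that the 60-70 Gy prescription and the organ totals omit the test dose by rule, and the documents do not say that. They do not say it is included either, and the two specific rules in Section 4 leave it out.

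The routine error is also modest. At +7.8% it reaches one 2 Gy fraction only if CLR 131 delivered about 2/0.078 = 26 Gy, and the treating physician has a 10 Gy range to choose from. The clear understatement belongs to a contingency, and the documents do not say how many subjects met it. The plan also considers a CLR 131 estimate above 60 Gy very unlikely. All of this stands and limits the point.

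The table omission is a matter of labelling. Section 4 states the flat 15 mCi alongside the dose table, and Section 6.5 records the mCi administered. A reader might infer that escalation was distorted, but all subjects receive the same test dose, so the ordering of levels and the Table 3 decisions do not change. A reader might also see a safety signal in Level 2 totals of 43.5-47.5 mCi/m² against the highest two-dose myeloma cohort in Section 2.1.3.3 (2 × 20 = 40 mCi/m²). That does not follow: the activity here is spread over about 2-5 weeks, and the phase 2 study in the same section gave 4 × 15 = 60 mCi/m² over 10 weeks.

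**Conclusion.** The concern holds for the two rules in Section 4. The single-injection rule understates the CLR 131 tumor dose in every case modelled, by about 11-20%, 20-28% and 29-32% at 7, 14 and 28 days. These figures are for Level 1 at BSA 2.0 m² and rest on equal Gy per mCi and shared kinetics. For two doses within the 7-14 day window the error is about −7% to +14% of the CLR 131 part, its sign is not fixed, and it depends on a doubling step that the plan does not state.

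A reader might go on to infer that a cord or brainstem limit was breached. The documents give no tumor, cord or brainstem Gy per mCi, so neither an overdose in Gy nor a breach can be claimed. The point deserves correction but does not undermine the dose-finding.

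**What to change.** **Dose rules.** In Section 4, replace both phrases with *all CLR 131 administered, including the test dose*, and say the same in Sections 6.8 and 6.8.4. Fit the post-dose-1 curve as A1·k(t) + 15·k(t + gap), where k is one kinetic function per mCi that includes uptake. Take the cumulative dose as (15 + A1 + A2) times the integral of k, with A2 the second treatment activity, or 0 if it was not given.

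Where that fit is not possible, multiply the unscaled dose-1 integrated dose by (15 + A1 + A2)/(A1 + 15f). Report the range from f = 0 to a slow-uptake case. Do not cap f at 2^(−gap/8.02), because slow uptake exceeds it (0.670 against 0.546 at 7 days). Use f = 0, which gives the highest dose, for organ limits. At Level 1, BSA 2.0 m², 14 days and two doses, the factor is 77.4/31.2 = 2.48 at f = 0 and 77.4/(31.2 + 15 × 0.372) = 2.10 with slow uptake. Do not apply it to a figure already scaled to two doses.

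For subjects who received only the test dose there is no dose-1 curve. Record the 15 mCi and claim no Gy figure.

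**Reporting.** Describe each dose level and the MTD as the 15 mCi test dose plus two treatment doses, and list each subject's gap, total mCi and mCi/m².

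**Cost.** Protocol wording, and a recalculation from the dosing records and existing scans. No extra scan, subject or change of dose is needed. Accrual closed in April 2022, so the change applies to re-analysis and reporting. The drawback is that the Gy results carry a model-based range.

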5 STUDY ENROLLMENT AND WITHDRAWAL

5.1 Number of Subjects

Up to 12 subjects treated at the MTD are planned for the study. The number of subjects in the expansion cohort will depend on the number of subjects treated in the mTPI-2 design (Section 14.2). Adult men and women of all races and ethnic groups are eligible for this trial.

5.2 Inclusion Criteria

In order to be eligible to participate in this study, an individual must meet all of the following criteria:

1. Subject must be informed of the investigational nature of the study and must be able to sign a written informed consent.
2. Subjects with histologically or cytologically confirmed solid malignancy that has recurred in the head and neck (above the clavicles) region, e.g., subjects with recurrent cutaneous squamous cell carcinoma, salivary gland tumors or esthesioneuroblastoma are eligible for this clinical trial.
3. Subject is 18 years of age or older.
4. Subjects must have undergone previous curative intent therapy, with radiation as a primary or adjuvant therapy.
5. Subjects may have distant metastatic disease, as long as the locoregional site of recurrence is deemed eligible for radiation therapy, and treatment of the loco-regional disease is deemed as taking precedence over treatment of the remaining systemic disease.
6. Subjects must have at least one evaluable (measurable or non-measurable) recurrent lesion that is amenable to radiation therapy.
7. Subjects must demonstrate uptake of CLR 131 via SPECT/CT imaging, as determined by the study radiologist, in the specified site of recurrent/metastatic disease that is to be treated with radiation therapy. There is a subset of up to 6 patients who may continue with CLR 131 treatment without uptake on the SPECT/CT scan after the test dose.
8. Subjects must have an ECOG performance status of 0 – 1.
9. Subjects must have a life expectancy of at least 6 months.
10. The subject has adequate hematologic function, as evidenced by:
 - an absolute neutrophil count (ANC) $\geq 1500 / \mu\text{L}$
 - hemoglobin $\geq 9 \text{ g/dL} (5.58 \text{ mmol/L})$
 - and platelets $\geq 100,000 / \mu\text{L}$
 - If full-dose anticoagulation therapy is used, platelets $\geq 150,000 / \mu\text{L}$ are required.

- If subject is on full-dose anticoagulation therapy, the anticoagulation therapy must be reversible, and reversal of the anticoagulation therapy must not be life-threatening, as judged by the investigator.

11. The subject has adequate renal function as defined by:

- serum creatinine \leq 1.5 times the upper limit of normal (ULN) or Cockcroft-Gault calculated creatinine clearance \geq 60 ml/min

12. The subject has adequate hepatic function as defined by:

- total bilirubin \leq 1.5 mg/dL (25.65 μ mol/L)
- aspartate transaminase (AST) and alanine transaminase (ALT) \leq 3.0 times the ULN

13. Women of childbearing potential (WOCP) have a confirmed negative urine pregnancy test within 24 hours prior to test dose of CLR 131.

14. Subjects must use a medically acceptable method of birth control such as an oral, implantable, injectable, or transdermal hormonal contraceptive, an intrauterine device (IUD), a double barrier method (condoms, sponge, diaphragm, or vaginal ring with spermicidal jellies or cream), or total abstinence during the study participation and for 6 months after last dose of study drug. Women who are postmenopausal for at least 1 year or surgically sterile (bilateral tubal ligation, bilateral oophorectomy, or hysterectomy) are not considered to be WOCP.

15. Men who are not surgically or medically sterile agree to use an acceptable method of contraception. Male subjects with female sexual partners who are pregnant, possibly pregnant, or who could become pregnant during the study must abstain from intercourse for three weeks after each CLR 131 dose and agree to use condoms at least 6 months after the last dose of study drug. Total abstinence for the same study period is an acceptable alternative.

